**1. PROJECT TITLE**

The Effects of Organic Triphala and VSL#3 Probiotic Supplementation on Stool Microbiome Profiles and Inflammation in Healthy Elderly Subjects ("TRIPH2017")

**4. ESTIMATED DURATION OF THE STUDY**

2 years

**5. LAY LANGUAGE SUMMARY OR SYNOPSIS (no more than one paragraph)**

Normal aging can lead to loss of gut microbial biodiversity which is linked to inflammaging and immunosenescence or the loss of immunocompetence. Probiotics, such as VSL#3®, and certain herbal supplements such as *Triphala* are associated with restoration of gut community architecture, increased gut barrier function and decreased inflammation. The present project will examine the potential benefits of a synbiotic (which denotes a prebiotic plus probiotic, and in this study, is an herbal prebiotic plus probiotic) intervention (8 weeks of supplementation) on gut microbiome profiles assessed via stool, inflammatory blood markers, and questionnaires about gastrointestinal health and mood. In this exploratory study, we will examine psychological and physical functioning at baseline and after 8 weeks of supplementation with synbiotic, *Triphala* alone, or placebo.

**6. SPECIFIC AIMS**

Primary Aim: In healthy, cognitively intact elderly subjects, determine the effects of an 8-week synbiotic supplement intervention on the stool microbiome (pre- and post-intervention) as compared to *Triphala* alone and placebo.

Secondary Aim: In healthy elderly subjects, examine the effects of an 8-week synbiotic supplementation intervention on inflammatory blood markers compared to herb alone or placebo.

Exploratory Aim 1: In healthy elderly subjects, examine the effects of an 8-week synbiotic intervention on gastrointestinal and psychological health via questionnaires compared to herb alone or placebo.

**7. BACKGROUND AND SIGNIFICANCE**

The elderly (persons aged 65 years or older) represent the fastest growing segment of the human population (15% of total US population). Among health care costs for older Americans, 95% are related to chronic diseases. The average senior spends about 3 times more in personal health care compared to working age adults [1]. The elderly are susceptible to inflammaging, or chronic inflammation resulting from a dysregulated balance between pro- and anti-inflammatory processes, as well as immunosenescence (reduced immune responsiveness) that leads to increased susceptibility to infection. The elderly are also known to be susceptible to damaging effects of free-radicals that may be produced in greater quantities in the aged due to chronic inflammatory processes.

Herbal remedies represent some of the most ancient medicines and are considered powerful means of maintaining human health and homeostasis. *Triphala* is a well-recognized Ayurvedic polyherbal medicine containing three beneficial plant species with known benefits that include the reduction of inflammation through

powerful antioxidant properties and immunomodulatory effects. The increased popularity of herbal remedies such as *Triphala* has led to dramatic improvements in the processing of crude plant materials that serve to maximize the absorption of otherwise poorly absorbed plant components. Despite these improvements, these preparations still display pronounced variability in efficacy which is likely related to the natural variation in composition of gut microbiota species that catalyze the biotransformation of herbal components. This response variability is not unique to herbs and in fact may be the case for virtually all health-promoting compounds ingested by humans (e.g. polyphenolic compounds derived from plants). For example, it is known that phytochemicals in *Triphala* such as quercetin and gallic acid promote the growth of Bifidobacteria and Lactobacillus while inhibiting the growth of undesirable gut residents such as *E. coli*. In addition, lactic acid bacteria possess enzymatic activity (e.g. tannase) to degrade plant tannins such as gallic acid contained in *Triphala*. There is extensive research on *Triphala*, which has demonstrated both safety and efficacy [2].

Our administered probiotic formulation co-administered with *Triphala* (the synbiotic) will contain species from 2 bacterial taxa that are generally lost in the elderly gut microbiota in genera Bifidobacteria and Lactobacillus. Both species have been approved for use by FDA (GRAS or generally regarded as safe) and have general association with human health; the particular probiotic formulation to be administered in this project is the widely clinically studied VSL#3® probiotic capsule, which contains both Lactobacillus and Bifidobacteria [3-5]. To our knowledge, no synbiotic (combination therapy of prebiotic and probiotic) developments targeting the elderly population have been described. The benefits of these taxa for the elderly are numerous. The widespread capacity of the Bifidobacteria to metabolize polyphenolic compounds (e.g. esters, glycosides or polymers) into bioactive metabolites with strong antioxidant activities and their impact on human health make them an attractive target. Both Lactobacillus and Bifidobacteria have been shown to increase lifespan in animal models as well as reduce inflammation in both humans and animal models [6-13]. Among many health benefits, Lactobacillus prevents oxidative DNA damage in human-derived colon cells and produces metabolites that are important mediators in the prevention of colorectal cancer [14-15]. Changes of the gut microbiota in elderly appear to involve a reduction in numbers of Lactobacilli and Bifidobacteria and an increase in numbers of potentially pathogenic species that lead to gastrointestinal disorders, inflammation, and infection [16]. Elevated Bifidobacteria levels are beneficial at all ages, including boosting the declining immune systems of the elderly [17]. Indeed, the level of Bifidobacteria in the gut is anti-correlated with serum levels of inflammatory TNF $\alpha$  and IL-6. Probiotics containing Bifidobacteria have been shown to positively modulate the microbiota of the elderly. Similarly, prebiotic treatments have led to similar effects [18-20]. For example, galacto-oligosaccharide prebiotic treatment of elderly subjects resulted in an increase in Bifidobacteria levels in the gut [21]. Inulin type fructans (i.e. prebiotics) are naturally occurring polysaccharides that are indigestible by humans. Inulins and similar fructans in *Triphala* induce a bloom of Bifidobacteria and Lactobacillus in the gut and have therefore been the subject of intensive study. Similarly, oligofructose prebiotic treatment of human subjects decreased the colonization by *Clostridium difficile* and was accompanied by reductions of relapse and hospital stay duration [22]. Thus, opportunities to improve human health and immunity through the modulation of the gut microbial communities by dietary supplement intervention remain highly promising for anti-aging and reducing morbidity and mortality associated with infection in the aged.

Our overarching research goal is to help reduce early morbidity from aging and mortality associated with infection in the aged by developing probiotics with the potential to enhance the health benefits of *Triphala* to reverse chronic inflammation and stimulate immune robustness. Our project is based on the hypothesis as well as *in vitro* data from our laboratory which demonstrate that the bioactivity of *Triphala* is elicited by the gut microbiome to generate a widened spectrum and abundance of anti-inflammatory compounds. We reason that the *Triphala*-induced benefits to both the elderly as well as persons of all ages can be enhanced by co-administration of specific probiotic species. *Thus, we hypothesize that probiotic formulations consisting of bacterial species capable of mediating the increased digestion, bioabsorption and bioactivity of Triphala will increase and make more uniform the response and impact of Triphala treatment on human populations. We hypothesize that the potent anti-inflammatory Triphala when co-administered with VSL#3 will further reduce inflammation and promote a healthier gut community architecture in the elderly.*

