**Measures of gut microbiome and treatments received.**

**Treatments:** Two grams of organic *Triphala* powder (Banyan Botanicals, Inc.) alone or with 1 capsule VSL#3® (VSL Pharmaceuticals, Inc.) probiotic taken with a few ounces of room temperature water in the morning and at bedtime, or placebo capsule taken morning and evening. Participants will be provided their synbiotic or placebo capsules during the T1 session. VSL#3® is a clinically validated probiotic that is commonly prescribed by UCSD GI physicians to help restore gut microflora.

**Gut microbiome assessment:** Participants will be mailed a stool collection kit prior to T1 and asked to bring their morning stool sample during the T1 and T2 assessment sessions.

**Blood marker assessment:** Participants will donate 1 vial of blood during the T1 and T2 assessments with the licensed phlebotomist.

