## **Assessment Outcomes**

Outcomes Hypothesis: Feasibility, treatment expectancy/satisfaction, retention, and adherence.

Recruitment rates will be recorded and new recruitment strategies will be formulated to overcome barriers presented by decliners for a future study. Treatment expectancy and satisfaction - 6 item credibility/expectancy questionnaire (CEQ) will be utilized. Retention (% of drop-outs) will be recorded, and exit interviews will be administered to determine reasons for drop-out. Adherence to intervention will be derived from T1 and T2 presence.

Outcomes Hypothesis: Objective measures of gut microbiome health.

*16S rDNA Sequencing:* Stool samples will be analyzed to identify alterations in the gut microbiota community structure by 16S rDNA sequencing. This experimental design will allow us to assess the efficacy of *Triphala* and probiotic species to positively modulate inflammaging and immunosenescence. We will also assess a panel of 30 cytokine/chemokines/lymphokines for this purpose. Finally, our study design permits us to evaluate potential synergistic interactions between the probiotic species and *Triphala*.

Outcomes Hypothesis: Objective measures of inflammatory status.

*Blood pressure (BP):* 3 resting automated BPs will be taken (Dinamap 1846SX) and averaged.

*Biomarkers:* Blood samples will be obtained by a licensed phlebotomist from a mobile phlebotomy service, Veni-Express in SOM Building 4's Clinical Rooms. Serum heparin or EDTA-preserved plasma will be stored at -80° C until assay in [name] laboratory space MTF-418. Inflammatory biomarkers will be assessed by ELISA (MSD, Minneapolis, MN).

For those participants who specifically consent to tissue banking in the ICF, their samples will remain in storage in [name] laboratory space MTF-418 after the end of this study. These blood and stool samples will remain under the sole control of the PI and may be investigated later for other inflammation-related biomarkers and gut microbes.

Exploratory Outcomes Hypothesis: Health-related behaviors.

*Pittsburgh Sleep Quality Index (PSQI):* A self-report of sleep quality and disturbances over a 1-month period.

Nineteen items generate seven "component" scores. The sum of scores yields one global score;

*Fruit/Vegetable/Fiber Screen and Fat Screen:* Rapid screeners with high correlations for total fat, saturated fat, cholesterol, fruit/vegetable intake.

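### A synbiotic-arm difference in stool Lactobacillus or Bifidobacteria may be recovered VSL#3, and cannot by itself show a healthier gut community

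*Combined protocol and SAP*

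**What the plan says.** Section 6 makes the primary aim a pre/post comparison of the stool microbiome under the synbiotic with Triphala alone and with placebo.

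Section 7 says that the probiotic "will contain species from 2 bacterial taxa that are generally lost in the elderly gut microbiota in genera Bifidobacteria and Lactobacillus", and identifies it as VSL#3, "which contains both Lactobacillus and Bifidobacteria". It presents higher levels of these genera as beneficial. Its hypothesis is that Triphala given with VSL#3 "will further reduce inflammation and promote a healthier gut community architecture in the elderly".

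In Section 9, the treatment paragraph describes the "probiotic taken with a few ounces of room temperature water in the morning and at bedtime". Experimental Conditions gives VSL#3 to the synbiotic group only. Participants are "asked to bring their morning stool sample during the T1 and T2 assessment sessions", and no other stool sample is mentioned. Assessment visits places T2 in the post-intervention period; the Analysis Plan is more specific and puts the second time point directly after treatment.

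On the assay, Assessment Outcomes says: "Stool samples will be analyzed to identify alterations in the gut microbiota community structure by 16S rDNA sequencing". The Analysis Plan applies two-sample t-tests to change scores, O'Brien's test, and a mixed model with a group-by-time interaction. No text describes a washout, sequencing of the product, a strain-level or viability method, or an analysis that sets the administered organisms apart.

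**The concern.** 16S sequencing reads bacterial DNA in the sample. It does not show whether an organism lives in the gut or was swallowed and is passing through, nor whether it is alive. One arm swallows organisms from two genera up to about the time of the second sample, and those are the genera whose rise the protocol regards as favourable. The capsule's contents and the hoped-for direction of effect therefore coincide.

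Randomization does not remove this, because the assigned product causes it. The Triphala-alone arm does not control for it, because that arm receives none of the organisms. All three planned analyses would register recovered product as a treatment effect.

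What is at stake is the interpretation. Section 9 (Sample Size and Power) says that the findings will inform a larger trial. If recovery of the capsule is reported as a changed gut community, that trial would be designed on a wrong premise.

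**Working it through.** **1. The plan's own figure.** The plan gives no figure for carriage. Its only related number is 80% power at d = 0.75 with 60 completers (two-sided alpha 0.05). Section 10 gives 20 per group. For 20 v 20 the non-central t calculation gives 63.7%, so 80% is not reproduced; 30 v 30 gives 81.5%. That is a separate matter and this point does not depend on it.

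**2. Rejection when only the product moves the score.** Inputs: n = 20 per arm (Section 10) and a two-sided 5% t-test on change scores (Analysis Plan). The shift d, in SDs of the change score, is assumed.

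Non-centrality = d / √(1/20 + 1/20) = d / 0.3162, with 38 degrees of freedom. The observed difference must exceed 0.64 SD to be significant.

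| Assumed shift d | Non-centrality | Rejection, residents unchanged |
|---|---|---|
| 0 | 0 | 5% |
| 0.25 | 0.79 | 12% |
| 0.5 | 1.58 | 34% |
| 0.75 | 2.37 | 64% |
| 1.0 | 3.16 | 87% |
| 1.5 | 4.74 | 99.6% |

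**3. What might produce such shifts.** Let p be the baseline share of the two genera and f the share of stool reads that come from the product. With residents unchanged, the shift in ln relative abundance is ln[(p(1 − f) + f)/p], and dividing by the SD of the ln-change gives d. For p = f = 2%: (0.0196 + 0.02)/0.02 = 1.98, and ln 1.98 = 0.68. With SD = 1.0 that is d = 0.68 and 56% rejection.

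Rejection for 20 v 20 with SD = 1.0 (p, f and the SD are all assumed):

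| Baseline share p | f = 0.1% | 0.5% | 1% | 2% | 5% |
|---|---|---|---|---|---|
| 0.5% | 9% | 57% | 92% | ~100% | ~100% |
| 2% | 5% | 10% | 23% | 56% | 97% |
| 5% | 5% | 6% | 8% | 17% | 54% |

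At p = f = 2%, changing the SD from 0.75 to 1.5 moves rejection from 80% to 29%. At f = 0.1% it stays between 5% and 12% over every baseline and SD tried (0.75, 1.0, 1.5). The distortion thus runs from negligible to decisive, and nothing in the plan would show which case applies.

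**The case against.** **The plan does not say that a rise in these genera confirms the hypothesis.** This stands. A reader might infer that any microbiome change would be counted as success, but no such rule is written. Section 6 asks about the effect on the stool microbiome, and on that literal reading recovered organisms are a real effect of the product on stool content. Raising these genera may also be wanted. The problem arises only in moving from that result to a healthier community.

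**No primary metric is named.** This also stands. A reader might infer that the synbiotic arm can win the primary comparison on product alone. The documents do not support that: they refer to community structure and nowhere make the two genera the primary measure. A genus-level score is directly exposed, while diversity or whole-community distance may be much less so.

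**The rejection rates follow from assumed shifts.** Correct. The documents give no organism count per capsule, baseline abundance or SD, nor the interval from last capsule to T2 stool. The rates are illustrations, not estimates.

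**Filtering could hide the effect under study.** This is the strongest objection. Section 7 expects Triphala constituents themselves to raise both genera, and 16S may not separate product organisms from resident relatives. Removing matching variants would remove that signal too. The filtered analysis therefore belongs beside the full one as a sensitivity analysis and should not replace it.

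**It is an exploratory pilot.** True, but limiting what is concluded suits a pilot.

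**Conclusion.** The concern holds as a limit on interpretation. Product in one arm only, stool taken directly after treatment, an assay that cannot tell swallowed from resident organisms, and no step to separate them together mean that a synbiotic contrast involving Lactobacillus or Bifidobacteria may partly or wholly reflect recovery of VSL#3. Such a difference cannot on its own support the hypothesis that the combination will "promote a healthier gut community architecture in the elderly".

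The size is unknown. With residents unchanged, rejection ranges from 12% to 99.6% for assumed shifts of 0.25 to 1.5 SD in a genus-level score, and it is near the nominal 5% if product reads are very sparse. It would be wrong to quote only the upper figures as the plan's false-positive rate. The conclusion rests on reading T2 as falling directly after dosing, which is the most specific wording given. Only the two microbiome contrasts that include the synbiotic arm are exposed; Triphala versus placebo and the blood markers are not.

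**What to change.** Prespecify, before the sequence data are analysed, that each microbiome contrast involving the synbiotic arm is reported in two forms:

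- on all reads;
- as a sensitivity analysis, after removing sequence variants that match the organisms declared for VSL#3 and re-normalising, with the same filter applied to all arms and both visits so that the filter itself creates no difference.

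Fix the list of declared organisms in advance, since the protocol names only the genera.

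State the rule for conclusions. Claim a change in community architecture beyond delivery of the product only if the effect persists after filtering. Otherwise, report a rise confined to product-matching taxa as consistent with delivery, and as neither establishing nor excluding resident change.

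The cost is one extra analysis of data already planned, with no change to treatment, visits or samples. The drawback is that the filtered version also discards some true resident signal, including any Triphala-driven bloom of these genera. A null filtered result must therefore not be read as no effect.

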## 8. PROGRESS REPORT

N/A

## 9. RESEARCH DESIGN AND METHODS

**Recruitment.** A total of 75 participants will be recruited from UCSD ADRC. We aim to recruit approximately 20 eligible individuals per group (1. synbiotic, 2. herb alone, and 3. placebo control) from UCSD ADRC.

**Screening.** After written consent, patients will undergo a medical history intake to determine eligibility. Along with study participants' referring providers, ADRC will provide oversight in determining whether potential subjects are eligible according to the following criteria:

**Inclusion criteria:**

- 1) Cognitively intact;
- 2) Able to give informed consent in English;
- 3) Medical clearance by their doctor;
- 4) > 60 years of age.

**Exclusion criteria:**

- 1) Alzheimer's Disease or other neurodegenerative disease such as Parkinson's Disease;
- 2) Current use or use in the past 3 months of antimicrobial or steroid drugs;
- 3) Medical conditions affecting immune status (e.g., heart failure, inflammatory bowel disease, hepatitis C, HIV);
- 4) International travel in the past 3 months.
- 5) Previous known side effect or negative reaction to VSL#3 or *Triphala*.

Note that heart failure, inflammatory bowel disease, hepatitis C, and HIV patients are excluded due to these diseases featuring variable and significantly altered immune status and gut microbiome, which are the main outcome measures of the study. This pilot study seeks to identify relatively healthy elderly subjects to assess these markers in the context of dietary supplementation.

**Assessment visits.** Assessment personnel will be naive to the participant group assignment. Testing will take place at SOM Building 4. At T1 (baseline): participants will 1) review their study responsibilities with the opportunity to reconsider participation 2) provide a stool and small blood sample for biomarker assessment; 3) complete psychosocial measurements via questionnaires; 4) receive group assignment instructions at the end of the visit. Measures will be repeated at T2 (post-intervention period).

**Randomization.** A computer-generated randomization algorithm will determine group assignment to ensure that participant demographics are evenly distributed across study conditions.

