#### Additional Measures

Age, gender, socio-economic status, ethnic group, relationship status, education, body-mass Index and waist-hip circumference will be recorded. If for medical reasons subjects alter medications, it will be recorded via a monthly tracking form that the subject can submit.

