**Exclusion criteria:**

- 1) Alzheimer's Disease or other neurodegenerative disease such as Parkinson's Disease;
- 2) Current use or use in the past 3 months of antimicrobial or steroid drugs;
- 3) Medical conditions affecting immune status (e.g., rheumatoid arthritis, heart failure, hepatitis C, HIV);
- 4) Individuals diagnosed with Diabetes Mellitus
- 5) International travel in past 3 months.
- 6) Previous known side effect or negative reaction to VSL#3 or *Triphala*

Obtained research material will include vital signs, peripheral blood and plasma (processed and stored in Core Laboratory until assay), stool, and psychological and health behavior questionnaires.

All data will be obtained from recruited subjects for research purposes only. Data will be collected specifically for the proposed research project.

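### Current users of probiotics, prebiotics or Triphala stay eligible and no supplement-use variable is specified, so the estimated effect is likely to be attenuated by an unknown amount

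*Combined protocol and SAP*

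**What the plan says.** The eligibility criteria appear three times: in Section 9 (Research Design and Methods), Section 10 (Human Subjects) and the telephone screen in Section 12 (Informed Consent). All three carry the same drug item, "Current use or use in the past 3 months of antimicrobial or steroid drugs", and all three exclude recent international travel. The only criterion that mentions the study products is "Previous known side effect or negative reaction to VSL#3" or to Triphala. It removes people who reacted badly and leaves in those who take the products without trouble. The Section 10 list adds "Individuals diagnosed with Diabetes Mellitus" but says nothing about supplements.

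The nearest records of supplement use are these:

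- Section 9, Screening: "patients will undergo a medical history intake to determine eligibility". Its content is not described.
- Section 9, Additional Measures: "If for medical reasons subjects alter medications, it will be recorded via a monthly tracking form that the subject can submit".
- Section 9, Assessment Outcomes: brief diet screeners for fruit, vegetables, fibre and fat, with no supplement item described.
- Section 11: chart medication lists, used to find candidates and not named as a study variable.

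Under Treatments, Section 9 describes VSL#3 as "commonly prescribed by UCSD GI physicians to help restore gut microflora".

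The analysis compares change scores by two-sample t-tests and fits a mixed model with a subject-specific intercept. It promises to control for baseline variables that differ between groups. Supplement use is not named as a covariate, a balancing factor or a sensitivity analysis.

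**The concern.** Section 9 justifies its disease exclusions by their effect on immune status and the gut microbiome, which are the trial's main outcomes. Section 7 says that Bifidobacteria-containing probiotics shift the microbiota of older people and that prebiotics act similarly. By that reasoning, taking a study product or a close relative of it matters at least as much as recent travel, yet it is not addressed.

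Three mechanisms follow:

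1. A participant who already takes such a product may change less when given active treatment.
2. A probiotic user assigned to Triphala alone takes roughly what the synbiotic arm takes. That blurs the synbiotic-versus-Triphala comparison in the Primary Aim and the search for synergy.
3. A placebo participant who starts a product during the 8 weeks moves the placebo arm.

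Each tends to pull the estimated difference towards zero. Without a planned record, a chance imbalance in users at 20 per arm could be neither seen nor adjusted for. The results are meant to inform a larger trial, so an attenuated estimate could carry over into that trial's planning.

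**Working it through.** **Inputs from the plan (Sections 9 and 10).** Cohen's d = 0.75; two-sided alpha = 0.05; stated power 80%; 60 completers in three groups of 20; 75 recruited with 20% drop-out.

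**Inputs that are assumptions.** q is the share of participants already using such products, taken as 10%, 20% or 30%. r is the fraction of the normal response that users keep, taken as 0 or 0.5. The documents give neither.

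**Step 1: the plan's own figures.** Recruitment reproduces: 60 / (1 − 0.20) = 75. Power does not. For two arms of n, the non-centrality is d × √(n/2).

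- n = 20: 0.75 × √10 = 2.37, and non-central t power is 64%.
- n = 30: 0.75 × √15 = 2.90, and power is 81.5%.

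The stated 80% therefore fits two groups of 30, not the planned pairwise comparison of 20 with 20. That is a separate error. The reference for this point is 64%.

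**Step 2: dilution.** With the SD held constant, observed d = 0.75 × [1 − q(1 − r)].

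| q | r = 0: d | power, 20 per arm | r = 0.5: d | power, 20 per arm |
|---|---|---|---|---|
| 0% | 0.75 | 64% | 0.75 | 64% |
| 10% | 0.75 × 0.90 = 0.675 | 55% | 0.75 × 0.95 = 0.7125 | 59% |
| 20% | 0.75 × 0.80 = 0.60 | 46% | 0.75 × 0.90 = 0.675 | 55% |
| 30% | 0.75 × 0.70 = 0.525 | 37% | 0.75 × 0.85 = 0.6375 | 50% |

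**Step 3: does the loss depend on the power error?** No. On the 30-per-group reading with r = 0, power falls from 81.5% to 73%, 63% and 52%.

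**Step 4: which arm drives the loss?** Let a stable user's product add u to the outcome at both visits. A placebo user's change is then (baseline + u) − (baseline + u) = 0 on average, so stable use cancels from the placebo change score. The formula in Step 2 reflects only a reduced response to active product. It covers neither use started during the study nor the blurring of the herb-only arm.

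**Step 5: would covariate adjustment recover the effect?** No. Adjusting for baseline use leaves the average effect at 0.75 × [1 − q(1 − r)]. Recovering the effect in non-users needs a subgroup or interaction analysis. At q = 20% that means 0.20 × 20 = 4 users and 16 non-users per arm.

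**The case against.** A reader might infer more than the documents support in five ways.

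**The trial no longer answers its question.** The Primary Aim concerns healthy, cognitively intact older people and is not limited to people who take no supplements. The effect on top of usual habits is a legitimate reading, and randomisation keeps that comparison unbiased on average. Restricting to non-users is a choice of target population. This objection stands.

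**Placebo participants on an active product spoil the control arm.** Step 4 shows that stable use largely cancels from change scores. Only use begun during the 8 weeks would shift that arm. This stands too.

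**Supplement use will go unrecorded.** The documents show only that no record is specified. The history intake, the chart medication list, or participant instructions and telephone scripts that are not reproduced might catch some of it. None is stated to yield a variable for analysis.

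**Use must be common because VSL#3 is prescribed at the institution.** That statement gives no rate and concerns gastroenterology practice. Participants here are generally healthy people recruited through a different centre. Nor does excluding earlier bad reactions show that current users are expected; it reads as a safety criterion.

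**The no-response figures are the expected loss.** They are a worst case. The plan's hypothesis is that Triphala and VSL#3 together do more than Triphala alone, so a probiotic user newly given Triphala might still respond. The half-response columns are there for that reason.

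It can also be said that this is an exploratory pilot. That lowers the stakes but does not close the gap, which is cheap to close.

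**Conclusion.** The gap is real. Followed as written, the plan can enrol people who already take a study product or something similar, and it specifies no variable to identify them. The likely consequence is an attenuated estimate and a less clear synbiotic-versus-Triphala contrast. The documents do not support a claim of systematic bias or of false positive results.

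The size cannot be fixed from the documents. Over the assumed 10% to 30% users, power at 20 per arm lies between 59% and 37%, depending on the response that users keep, against 64% with none. A user share below 10% would cost less. These figures assume a constant SD and equal arms of 20.

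The fall from the stated 80% to 64% should not be attributed to supplement use. At 10% users with no further response, dilution costs about 9 points (64% to 55%), while the separate power error accounts for about 16 (80% to 64%).

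**What to change.** 1. Add current or recent use of probiotic, prebiotic or Triphala supplements to the exclusions in Section 9, Section 10 and the Section 12 telephone screen, in the same words. The investigators should set the window. Editing one list alone would add to the differences already present between them.
2. Ask participants not to start non-study products of this kind during the 8 weeks.
3. Record non-study supplement use at T1 and T2.

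The cost is one eligibility line in each list, one instruction, and one question at each visit. The recruitment pool also shrinks by whatever the share of users is. To randomise 75 people, the number of otherwise eligible candidates rises to 75 / (1 − q): 84, 94 or 108 at 10%, 20% or 30% users.

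If the investigators prefer to keep users, they should record use at both visits, balance baseline use in the randomisation algorithm, and prespecify a sensitivity analysis without users. Covariate adjustment is worth having because it reduces noise and the effect of chance imbalance, but it does not remove the dilution. Neither route restores the stated 80% power, which needs its own correction.
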